Aim 2: Evaluate the impact of home-based TeleNP on the differential diagnosis of typical and atypical AD. 2a. Is the neuropsychologist's diagnosis comparable across TeleNP and FF conditions? 2b. Does flexibility to incorporate additional tests (Flexible Assessment) that are not readily adaptable to video administration alter diagnostic conclusions? *Given that neuropsychologists' conceptualizations of patient presentations may differ from the referring neurologist, this Aim will appraise whether TeleNP results in the same diagnoses from neuropsychologists compared to FF (gold standard) conditions.*

Aim 3: Appraise the feasibility and acceptability of TeleNP in the evaluation of AD patients. 3a. What is the user experience of TeleNP by patients, care partners, neuropsychologists, and psychometrists? 3b. Are there barriers or unique benefits of TeleNP that may influence future use and scalability in clinical care? *This Aim will utilize mixed methods, including interviews about the user experience and surveys of intervention feasibility and acceptability, to address quantitative and qualitative aspects of TeleNP that may influence the pragmatic implementation of remote assessments in a future, definitive trial.*

II. Background and Significance:

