TeleNP= home-based teleneuropsychology using video administration; **Core Battery**= Interview + standard battery of neuropsychological tests administered in FF and TeleNP modalities. **Flexible Option** = Menu of tests administered in addition to Core Battery in FF condition; tests include measures less adaptable to TeleNP (e.g., physical/tactile stimuli). **Stakeholder Interview**: Structured interviews with neuropsychologists, psychometrist, and a subset of participants and care partners

Intervention Components:

Pre-Visit Call: The psychometrist will place a pre-visit call to the participant and care partner up to 5 days prior to the scheduled FF visit or TeleNP visit. For the FF condition, the participant will be reminded to bring their care partner to provide additional details regarding symptom history during the interview. For the TeleNP condition, the psychometrist will have sent/delivered a study tablet, to the patient's home between the recruitment/screening call and the pre-visit call. During this pre-visit TeleNP call, the psychometrist will remind the participant to include their care partner on the assessment day, as the care partner will be encouraged to assist with setting up their home testing environment and to provide additional details regarding history during the TeleNP

interview. A test video call will also be conducted during this session, and the psychometrist will assist with troubleshooting.

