Protocol and Core Battery (2 hours): In both conditions (FF; TeleNP), **the neuropsychologist will first conduct a structured, 30-minute interview with the participant and care partner, if available, which is a standard component of neuropsychological assessments.** The psychometrist will subsequently conduct a Core Battery of standardized neuropsychological assessments (see Data Collection below). The majority (60%) of clinical neuropsychologists employ psychometrists to administer their tests, thus our approach simulates clinical practice.²⁴ Tests in the Core Battery were selected based on: a) breadth: coverage of all primary domains (i.e., memory^{25, 26}, attention/executive functions^{27, 28}, visuospatial²⁹, and language functions³⁰); b) use in clinical practice: frequent use in neuropsychological evaluations with established, validated norms in older adult populations; c) availability of alternate forms: presence of alternate forms, where possible, for tests most sensitive to practice effects (e.g., memory, verbally-mediated executive measures); and d) adaptability to TeleNP: inclusion of tests that minimize use of physical/tactile stimuli; i.e., inclusion of tests that may be screen shared via remote video technology and/or permit the patient to utilize their own piece of paper. The psychometrist will score the Core Battery based on published normative data for an older adult population using an automated excel calculator and provide the demographic-adjusted scores to the neuropsychologist. The neuropsychologist will document their diagnosis and severity of the participant's presentation.

Assessment Modality Details:

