Face-to-face (FF) Assessment (control condition): The participant will undergo an in-person evaluation with the neuropsychologist and psychometrist at the Clinical & Translational Research Center (CTRC) or in Building 400 at CU-AMC. The standard protocol will be administered, including the interview and Core Battery. After completion of the Core Battery and submission of initial ratings, the supervising neuropsychologists may elect to have additional tests administered by the psychometrist as part of a Flexible Assessment. The Flexible Assessment will include a menu of tests that have physical/tactile stimuli (e.g., Design Fluency; Trail Making Test), all of which are excluded from the Core Battery due to lack of adaptability to video-based administration. Upon receipt of the scores from the Flexible Assessment, the neuropsychologist will complete a second form indicating any alterations to their diagnosis based on new information.

TeleNP Assessment (intervention condition): The participant will undergo a video-based TeleNP assessment using a HIPAA-compliant platform (e.g., Zoom). The participant will be at home using a study-provided tablet, and the neuropsychologist and psychometrist will administer the evaluation from either the CTRC or their CU-AMC office. During the scheduled TeleNP assessment, the standard protocol will be administered (i.e., interview and Core Battery). The psychometrist will assist with tablet collection at no direct cost to the participant (i.e., will provide a paid return box; alternatively, participant may drop off tablet if convenient to them)

Data Collection for Clinical Trial Participants:

Medical records:

--Participants will be asked to allow their past, current and future medical record information, to be placed in our RedCap database. The goal is to collect health information pertinent to cognitive functioning in older adults. Because concurrent medical conditions and treatments may impact the participants' health, it is likely that all pertinent past, current and future medical record information will be considered for inclusion in the RedCap database. This will include: symptom history and diagnostic considerations from the participants' neurology notes; laboratory results; health history (i.e., major medical problems); brain imaging results.

Demographics:

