--Participants' age, birthdate, sex, gender, education level (Years), race/ethnicity, prior occupation, etc. will be obtained. Participant's contact information and address will also be obtained to facilitate scheduling baseline and follow-up appointments.

Interview:

--Participant's symptom history will be documented on a standard data collection sheet during the interview portion.

Neuropsychological Testing, Core Battery (May not be given in its entirety):

- Cognitive/Mood Surveys:
 - Geriatric Depression Scale
- Cognitive Assessments:
 - Global:
 - MoCA, with alternate forms
 - Memory:
 - CVLT-II, with alternate forms
 - Benson Figure Recall / RBANS Figure Recall
 - Speed/Executive Functions:
 - Oral Trail Making Test
 - Oral Symbol Digit Modality
 - Digit Span, with alternate forms
 - Verbal Fluency, with alternate forms (FAS; BHR)
 - Color Word Inhibition
 - Language:
 - Sentence Repetition
 - Boston Naming Test-15 item, with alternate forms
 - Verbal Agility
 - WRAT Reading
 - Abbreviated Peabody Picture Vocabulary Test
 - Syntactic Comprehension
 - Visuospatial and Posterior Cortical Function
 - Judgment of Line Orientation (Short Form)
 - Benson Figure Copy / RBANS Figure Copy
 - Calculation Screen

Neuropsychological Testing, Flexible Assessment:

- Cognitive Assessments in addition to Core Battery (May not be administered in its entirety):
 - Grooved Pegboard
 - Clock Drawing Test
 - Rey-Osterrieth Complex Figure
 - BVMT
 - Navon Figures
 - Face Perception/Affect Naming
 - VOSP Number Localization
 - Design Fluency
 - Written Trail Making Test A & B

Surveys:

- 4-item measures of acceptability and feasibility
- 19-item modified UTAUT after TeleNP portion

Cognitive Composites, Neuropsychologist Diagnosis, and Interviews: See Outcome Measures Below

Data Collection for Care Partner Participants:

Demographics:

--Care partner's age, birthdate, sex, gender, education level (Years), race/ethnicity, prior occupation, etc. will be obtained. Participant's contact information and address will also be obtained to facilitate scheduling baseline and follow-up appointments.

Surveys:

- 4-item measures of acceptability and feasibility
- 19-item modified UTAUT after TeleNP portion

Interviews: See Outcome Measures Below

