F. Statistical Analysis Plan:

For **Aim 1**, we will adopt an equivalence testing framework. The null hypothesis is that there is an average difference of at least .5 SD units in the difference in the z-scores, where .5 SD defines a potentially clinically meaningful difference. The alternative hypothesis is that the mean of the

difference in the z-scores is zero. This is the reverse of standard statistical testing. We elected a .5 SD margin as an initial threshold for a clinically meaningful difference; the reason for this decision is that once an individual reaches a level deemed to be clinically significant impairment (e.g., mild impairment = -1.5 SD; moderate impairment =-2.0 SD), a change in .5 SD equates to a categorical difference in their overall severity rating. To conduct our equivalence test, we will compute the difference in the z-score between the FF and TeleNP conditions and compute the mean difference and a 90% confidence interval based on a t-test. This results in an equivalence test with an alpha=0.05. If the entirety of bounds of the 90% confidence interval are between (-.5SD, .5SD), then the two assessments will be considered equivalent. We will repeat this computation stratified by referring diagnosis (typical vs. atypical), and also by sex or race/ethnicity (white vs. non-White).

For **Aim 2**, we will compute a 3x3 table with the rows as TeleNP diagnosis and the columns as FF diagnosis to summarize the results. To assess the equivalence of TeleNP and FF for each condition we will create 3, 2x2 tables. For example, when assessing for differences in typical AD we will collapse over atypical AD and Not AD. Following prior work³⁵, we will compute the difference proportion of typical AD for the TeleNP and FF setting and construct a 90% confidence interval. A difference of proportions greater than 5% will be considered a clinically meaningful difference. If the 90% confidence interval is between (-5%,5%), then the two modalities will be considered equivalent. We will repeat this process for the two other neuropsychologist-determined categories (atypical AD, Not AD). We will conduct the same analyses, stratified by severity. We will assess whether the neuropsychologists' diagnosis is equivalent to the Flexible Assessment by repeating the above analysis using the Flexible vs FF diagnosis (i.e., diagnosis reported prior to initiating Flexible Assessment).

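### The Flexible Assessment menu mixes tests that seem deliverable by video with tests that do not, so the pooled Aim 2b comparison cannot separate the two

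*Combined protocol and SAP*

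**What the plan says.** Section I, Aim 2b asks: "Does flexibility to incorporate additional tests (Flexible Assessment) that are not readily adaptable to video administration alter diagnostic conclusions"?

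Section IV.B (Face-to-face Assessment) describes the added tests as having physical or tactile stimuli, with Design Fluency and Trail Making as its examples. On why they are not in the standard battery, it makes one statement for the whole menu: "all of which are excluded from the Core Battery due to lack of adaptability to video-based administration". The neuropsychologist may choose to use them once the Core Battery ratings are in, and then enters any change of diagnosis on a second form. The terminology list in the same section is looser: "tests include measures less adaptable to TeleNP (e.g., physical/tactile stimuli").

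Section IV.B (Protocol and Core Battery, criterion d) says what suits a test to TeleNP: "inclusion of tests that may be screen shared via remote video technology and/or permit the patient to utilize their own piece of paper". The Core Battery, which is given in both modalities, includes "Benson Figure Copy / RBANS Figure Copy", the matching figure recall, and Judgment of Line Orientation.

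The Flexible list under Data Collection has nine entries, among them Clock Drawing, the Rey-Osterrieth Complex Figure, Navon Figures and "Face Perception/Affect Naming".

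Section IV.F answers Aim 2b by "repeating the above analysis using the Flexible vs FF diagnosis". For each diagnostic category, this takes the difference in proportions after and before the Flexible tests, with equivalence declared if the 90% interval lies within ±5%.

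**The concern.** Aim 2b is about a particular kind of test, one that TeleNP does not readily deliver. Its analysis counts a change of diagnosis after any test on the menu. If the menu held only tests of that kind, the two would coincide. The listed menu appears to be mixed, so a change prompted by clock drawing or affect naming counts as evidence about tests that video handles poorly.

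The distinction matters for the definitive trial that this pilot is meant to inform. If changes follow tests that need physical material, some testing may have to stay in person. If they follow tests that can be shown on screen or drawn on the patient's own paper, the TeleNP battery could be widened instead. The pooled result does not tell these apart. The second form, as described, asks for the altered diagnosis and not for the test behind it.

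**Working it through.** **Step 1: the menu against criterion (d).** The documents give test names, not formats, so comparable Core tests serve as the benchmark.

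| Flexible test | Format, as far as the name or text shows | Nearest Core test | Appears to meet (d)? |
|---|---|---|---|
| Grooved Pegboard | apparatus | none | no |
| Design Fluency | named in the protocol as physical/tactile | none | no |
| Written Trail Making A & B | named in the protocol as physical/tactile | oral version only | no |
| Clock Drawing | drawing | figure copy | yes |
| Rey-Osterrieth Complex Figure | figure drawing | figure copy and recall | yes |
| Navon Figures | viewed stimulus | Judgment of Line Orientation | yes |
| Face Perception/Affect Naming | viewed stimulus | Judgment of Line Orientation | yes |
| BVMT | not described | figure recall, if drawn | plausibly |
| VOSP Number Localization | not described | Judgment of Line Orientation, if viewed | plausibly |

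Counting only tests whose names show the format gives 4/9 = 44%. Adding the two undescribed tests gives 6/9 = 67%. Either count conflicts with a statement about all of them.

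**Step 2: how many changes decide the result.** The plan gives no power, expected change rate or other figure for Aim 2b, so there is nothing to reproduce. Inputs from the documents are n = 80, a 90% interval and a ±5% margin. Assumptions are a paired Wald interval (the plan refers to prior work without naming a method), all 80 patients analysed, and no change counted where no Flexible test was chosen.

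With b patients moving one way into or out of a category and none moving back:

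- d = b/n
- SE = √(b − b²/n)/n
- interval = d ± 1.645 × SE

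One change: d = 1/80 = 1.25%; SE = √(1 − 1/80)/80 = 1.24%; interval -0.8% to 3.3%. Passes.

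Two changes: d = 2/80 = 2.5%; SE = √(2 − 4/80)/80 = 1.75%; interval -0.4% to 5.4%. Fails.

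**Step 3: sensitivity.**

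- Tango score interval, n = 80: the upper limit is 3.3% with no change and 5.4% with one, so a single change fails.
- Wald, only 40 patients given Flexible tests and analysed: one change gives 2.5% + 1.645 × √(1 − 1/40)/40 = 6.6%. Fails.
- Changes that cancel: with equal numbers each way, d = 0 and the half-width is 1.645 × √t/80 for t changes in total. This is 4.1% for t = 4 (passes) and 5.04% for t = 6 (just fails). The fragility is therefore to one-way changes.

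**The case against.** The strict statement about the menu rests on one sentence. The terminology list speaks only of a menu that includes less adaptable measures, which a mixed menu satisfies, and the aims use similarly soft wording. A reader might infer that the protocol claims these tests cannot be given by video. It does not. This softens the contradiction without removing it, because the Face-to-face paragraph says all, and the aim and its analysis treat the menu as one class.

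The classification is partly inference. The formats are not described, and criterion (d) is one of four considerations in choosing the Core Battery rather than a test-by-test definition. So it would be too much to say that most of the menu is deliverable by video. The drawing tasks are the firmest cases, because figure drawing is already in the Core Battery.

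A reader might also infer that the trial will attribute diagnosis changes to the video format. Nothing in the documents says so. Aim 2b is a before-and-after comparison within the FF visit, and modality is compared in Aim 2a on the Core Battery alone.

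Finally, TeleNP has no Flexible step, so added testing and test content would stay entangled even with a purely tactile menu. That stands as a limit on any causal claim about modality. With such a menu, however, each change would at least follow a test that TeleNP does not readily deliver, which is the Aim 2b question. The mixed menu breaks that link.

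**Conclusion.** The point holds in a limited form. The statement that all menu tests were left out of the Core Battery for want of video adaptability conflicts with at least 4, plausibly 6, of the 9 tests listed, judged by criterion (d) and by comparable Core tests. Because Section IV.F pools all changes, Aim 2b as analysed estimates the effect of optional additional testing, not of tests poorly suited to video.

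At n = 80, two one-way changes in a category are enough to fail the ±5% rule under the assumed Wald interval, and one is enough under the score interval. A change or two prompted by a test suited to video could therefore decide the result. How likely that is cannot be stated, because the documents give neither a change rate nor the share of changes that each kind of test would prompt.

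Aim 2a is untouched, and this is a sub-aim of a pilot. The change is still worth making, because the information about which test prompted a change is hard to recover later.

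**What to change.** 1. Before analysis, classify each of the nine Flexible tests under criterion (d) as adaptable or not adaptable to video, and put the table in Section IV.F.
2. On the existing second form, record which Flexible tests were given and which prompted any change of diagnosis or severity.
3. Keep the planned Flexible-vs-FF comparison, labelled as the effect of optional additional testing. Beside it, report changes by class: at least one non-adaptable test involved, or adaptable tests only. Draw any Aim 2b conclusion about tests poorly suited to video from that breakdown.
4. Reconcile the Face-to-face paragraph with the terminology list, criterion (d) and the listed menu.

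The breakdown should sit beside the pooled result and not replace it. Setting aside changes credited to adaptable tests would push the result toward equivalence on the rater's word alone.

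The cost is two fields on a form already in use, one classification table and one extra tabulation, with no added visits, tests or patients. The attribution is the rater's own and counts per class will be small, so the breakdown will be descriptive.

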Incorporation of Results into Clinical Care: Because the set battery used in the FF assessment uses validated tests that are normally used for these patients in clinical care, it is likely that patients in this study *will not* undergo a separate standard of care neuropsychological assessment. Therefore, a brief research overview of the results of the FF assessment will be provided to the referring neurologist and the participant after both conditions are complete (and posted to Epic Medical Record as a research note), for use in their clinical care. Based on a

national survey, the median time between neuropsychological assessment and completion of reports is 3 weeks; our proposed time is slightly longer than the median, but remains within an expected range for clinical reports.³¹ Of note, when considering the amount of time between referral and scheduled date of assessment in SOC (often on the order of months), our window will likely be shorter/faster than SOC given dedicate research time. If any safety, psychological or other signs of distress related to potential diagnosis of AD are noted during either assessment, appropriate referrals will be coordinated by Drs. [name] and [name]. Drs. [name] and [name] will coordinate with the neurologist to determine if prompt discussion of the first assessment is clinically prudent. The research note posted to Epic EMR will include a brief background/history, table of scores for FF condition, and summary/recommendations, consistent with standard of care approaches.

C. Outcome Measure(s):

Aim 1: Equivalence of Cognitive Test Results: *The goal of this Aim is to test the concurrent validity of cognitive measures across testing modalities and determine whether the test results differ based on referral diagnosis.* Z-scores will be calculated based on age-referenced normative data for each cognitive test (Table 1) in the Core Battery. For data reduction purposes, a mean z-score for each cognitive domain will be used (i.e., memory, executive functions, spatial abilities, language). This will allow us to address whether neuropsychological test results are equivalent across modality (i.e., FF vs. TeleNP) and whether complexity of referral impacts comparability of test results.

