Quantitative: To appraise feasibility of TeleNP, we will include measures of enrollment tracking (i.e., enrolled vs. decline), protocol assessment time, tracking of protocol adherence (i.e., completion of Core Battery), and presence of technological difficulties (e.g., termination of assessment due to technological difficulties). **The psychometrist will ask all patients (n=80) and associated care partners (up to n=80)** to complete validated 4-item Acceptability and Feasibility of Intervention Measures^{32, 33} after both conditions, and a 19-item UTAUT questionnaire (adapted to TeleNP) after the TeleNP condition to measure determinants of intention to use.

We will document the fidelity of assessment administration and scoring using a fidelity checklist in a random 20% sample of participants.

Costs and Payments

All costs associated with the implementation and maintenance of the study shall be supported by [name] grants. There is no charge to participants or participants' insurance for participation.

Clinical Trial participants will receive \$25 to compensate for their time after both visits are completed. Care partners will not be compensated.

C. Description, Risks and Justification of Procedures and Data Collection Tools:

Description of Risks:

Potential risks to participants, by intervention, including physical, psychological, social, cultural, financial, and legal risks: For both conditions, there are no expected physical or legal risks. Participants will be advised that the clinical trial is voluntary, and that they may obtain a clinical neuropsychological evaluation in lieu of the research study as part of standard of care.

Risks associated with neuropsychological assessments:

- Both conditions (FF [control] and TeleNP [intervention]): The potential risks associated with participation in the study are minimal and include the risk of anxiety and/or fatigue, boredom or frustration during the completion of the neuropsychological testing sessions. An additional potential risk is loss of confidentiality, which could lead to potential social or cultural risks, if personal sensitive information is shared outside of the intervention.
- TeleNP: For the TeleNP condition, there are no expected physical, social, cultural, financial or legal risks. One potential risk is loss of privacy and/or confidentiality, as described below. We will employ video-based assessments for the TeleNP section, using HIPAA-compliant platforms.

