Diagnosis: While neuropsychologists will be apprised of the study design, they will be blinded to the *specific* referral diagnosis (i.e., typical vs atypical AD); moreover, the neuropsychologist will be asked to provide *their own determination* and given the option of including “Not AD” as their provisional diagnosis. The goal of this approach is to minimize bias and circularity; however, it remains possible that neuropsychologist-specific effects will be present (i.e., tendency to rate participants as “complex”). We will assess in exploratory analyses whether there were provider-specific effects on outcomes. We acknowledge that the division of diagnoses into three categories (i.e., subjective concerns; MCI; dementia) does not fully map onto NIA-AA diagnostic criteria for MCI² and AD dementia¹; however, most neuropsychologists do not have access to fluid/PET biomarkers in clinical practice, thus our approach more pragmatically represents standard of care. Nonetheless, neuropsychologists often do provide specific diagnoses for complex phenotypes, including focal presentations (e.g., posterior cortical atrophy). As an exploratory strategy, we will consider providing an additional diagnostic field for the neuropsychologist to indicate specific considerations in their differential.

Statistical Analysis Framework: We are evaluating equivalence by examining mean Z-scores per cognitive domain, aggregated across multiple tests; however, individual tests have different test-retest reliabilities, which are often evaluated on a patient-specific level through the use of reliable change indices (RCIs). Given the pilot nature of this clinical trial, it is possible that a .5SD difference in mean domain score will not accurately reflect a clinically meaningful difference in individual test scores. As such, we will consider examining test-specific differences across modalities using published test-rest reliability.

Technological Difficulties: We have incorporated several approaches to minimize and troubleshoot technological difficulties, including a pre-visit test call, inclusion of care partner in the process, and provision of a study tablet to all participants. Consistent with Aim 3, **we will track technological issues throughout the study procedures to inform changes that might be beneficial to a larger clinical trial**. In addition, we will include a discussion during monthly team meetings regarding any technological issues that arise.

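### Does Aim 1 need a written rule for domain mean z-scores when a Core Battery test is missing at one visit?

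*Combined protocol and SAP*

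**What the plan says.** Section IV.C, Aim 1, sets out the scoring: "Z-scores will be calculated based on age-referenced normative data for each cognitive test (Table 1) in the Core Battery". These scores are then reduced so that "a mean z-score for each cognitive domain will be used (i.e., memory, executive functions, spatial abilities, language".

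Section F, Aim 1, gives the analysis: "we will compute the difference in the z-score between the FF and TeleNP conditions". A mean difference and 90% confidence interval follow, and equivalence is declared if the interval lies within ±0.5 SD. For the referral groups, section F adds: "We will repeat this computation stratified by referring diagnosis (typical vs. atypical").

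The test list in section IV.B is headed "Neuropsychological Testing, Core Battery (May not be given in its entirety"). Its memory block has two entries, the CVLT-II and "Benson Figure Recall / RBANS Figure Recall". It lists three visuospatial tests, five speed/executive tests and six language tests. Table 1, which section IV.C cites, is not in the text available for this review.

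The quantitative part of Aim 3 tracks Core Battery completion and technical problems such as "termination of assessment due to technological difficulties". Section E concedes that domain means may hide differences on single tests and says "we will consider examining test-specific differences across modalities".

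Neither the outcome section nor section F gives a minimum number of tests, a matched-test requirement or an imputation method.

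**The concern.** The outcome is a difference between two averages, and the plan itself allows for an incomplete battery. If each average is taken over whatever tests were completed, one patient's FF and TeleNP composites can describe different sets of tests.

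Randomised order does not protect against this, because loss caused by video follows modality and not visit order. Losing a low-scoring test by video raises the TeleNP composite and can hide a real TeleNP deficit, which is the error an equivalence test must guard against. Losing a high-scoring test creates a difference that is not there. A rule left open can also be chosen after the results are seen. The two-entry memory domain is the most exposed.

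**Working it through.** **1. The plan's own figure.** A 90% interval used for equivalence corresponds to two one-sided tests, each at (1 − 0.90)/2 = 0.05. This matches the alpha in section F. The plan gives no SD of the difference, power or missing-test rate for Aim 1, so nothing else can be reproduced.

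**2. Bias if available tests are averaged.** Let a domain have k tests, with the lost test g below the mean of the others.
- The full mean is (mean of others) − g/k. After the loss it is (mean of others). That patient's composite therefore shifts by g/k.
- If a net share f of patients lose the test in one modality only, the group difference shifts by f·g/k.

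The values of k come from the list in section IV.B; f and g are assumptions.

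| Domain | k | g | f | Bias (SD) |
|---|---|---|---|---|
| Memory | 2 | 1.0 | 10%, 20%, 30% | 0.05, 0.10, 0.15 |
| Visuospatial | 3 | 1.0 | 20% | 0.067 |
| Executive | 5 | 1.0 | 20% | 0.040 |
| Language | 6 | 1.0 | 20% | 0.033 |

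A gap of 0.5 SD halves every entry.

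**3. Effect on the verdict.** This is a patient-level simulation (6,000 runs) with k = 2, g = 1, an assumed complete-data difference SD of 0.75, and loss in TeleNP only. The 90% half-width at n = 80 with complete data is 0.186 × 0.75 = 0.14. Entries are the chance of declaring equivalence under available-test averaging.

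| Net loss | No true difference, n = 80 | No true difference, n = 40 | True deficit 0.5 SD, lower-scoring test lost, n = 80 |
|---|---|---|---|
| 0% | 100% | 99% | 5% |
| 10% | 100% | 97% | 14% |
| 20% | about 100% | 92% | 29% |
| 30% | 98% | 82% | 48% |

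**4. Equal loss.** With 10% loss of the same test in both modalities, the bias is 0, the SD rises from 0.75 to 0.81 and false equivalence stays at 5%.

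**5. Would a matched-test rule settle it?** Matched scoring averages only over tests completed in both modalities. If the modality effect is the same on every test, it holds false equivalence at about 5% in these scenarios. Now keep the mean true deficit at 0.5 SD but put 1.0 on the lost test and 0 on the other. Matched scoring is then biased by f × (1.0 − 0)/2, which is 0.05, 0.10 and 0.15 SD at 10%, 20% and 30% loss.

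| Net loss | Matched tests, false equivalence | Available tests, false equivalence |
|---|---|---|
| 10% | 14% | 29% |
| 20% | 27% | 64% |
| 30% | 43% | 90% |

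Matching reduces the bias but does not remove it when a test is lost because it works badly by video.

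**6. Does the plan supply f and g?**
- It gives no rate of one-sided loss and no level difference between tests in a domain.
- Section IV.B defines the Core Battery as a standard set given in both modalities, and selects its tests partly for use over video.
- Tests that need physical materials go to the Flexible menu, which is given in FF only and lies outside the Core Battery scores.
- A study tablet, a test call with troubleshooting and care-partner help all work against loss by video.

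**The case for a change.** The strongest case for a change is that missing tests are foreseen, technical termination arises naturally only by video, Aim 1 makes a formal declaration at alpha 0.05, and one sentence would close the gap at almost no cost. The arithmetic in steps 2 and 3 is sound, and pilot status does not excuse a biased comparison. The possible test-level analysis in section E is not a commitment and does not define the composite.

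What stands is that the rule is unwritten and that one obvious way of filling it could mislead. Three things weaken the step from there to a required change.

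- The harm depends on a scoring method the plan does not state, together with net one-sided loss and a level gap. The largest figures add the smallest domain, a 1 SD gap, up to 30% loss, a true deficit exactly at the margin, and loss in the masking direction. At a 0.5 SD gap and 10% loss, false equivalence at n = 80 is about 9%.
- The cited cause fits only in part. Terminating an assessment may remove whole domains or the visit, which drops the pair and does not change its test mix.
- The allowance for an incomplete battery may mean the same tests are left out at both visits. The text does not say, but matched composites would then follow.

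**Conclusion.** No change to the plan follows. The missing-test rule is unwritten, but this is detail that a competent analyst of paired differences can supply: compare the same tests at both visits, fix that in the scoring program before modality results are seen, and read the result beside the completion data that Aim 3 already collects. Writing the rule down would be harmless clarification, and would not correct any stated method.

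The possible bias is f·g/k. For memory it is 0.05 to 0.15 SD at 10% to 30% net loss with a 1 SD gap, and less in the larger domains. With no true difference, the n = 80 conclusion barely moves; an n = 40 referral stratum loses more, from 99% to 82% at 30% loss. Serious false equivalence needs a true deficit near the margin as well as loss in the masking direction.

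These sizes rest on assumed f, g and SD, and on test counts from the list in section IV.B, because Table 1 could not be checked. The conclusion would weaken if completion proved clearly lower by video for particular tests. In that case a matched-test rule alone would not be a full answer either.
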